2. Treatment procedures

During the LR procedure, patients were placed in the supine position, often under general anesthesia of the trachea. Operators fully exposed the surgical field and explored the location of the tumor and vascular anatomy. After blocking the first liver portal, operators ligated the liver section blood vessels and bile ducts, assessed the distance between lesions, and ensured residual liver volume. Multiple tumors were removed by en bloc resection or multiple LR with good liver function, including indocyanine green (ICG) clearance tests ^[6].

During the TACE procedure, an emulsion of mixtures of lipiodol (3–30 ml) and chemotherapeutic drugs was injected, including doxorubicin (10–50 mg), cisplatin (10–110 mg), epirubicin (10–50 mg), or oxaliplatin (100–200 mg). Afterward, either a gelatin sponge or polyvinyl alcohol foam (PVA) particles were introduced to embolize tumor-feeding vessels either selectively or super-selectively ^[7].

3. Model development

According to survival algorithms in the existing literature, 10 kinds of available AI models were developed in the training set. The details of data preprocessing and model development are shown in Supplement 1. To reduce the overfitting of survival models, the AI algorithms in the training cohort were developed by adopting K-fold cross-validation. In each fold, hyperparameter optimization was tuned by an exhaustive cross-validation grid search, and the models were refitted in the training set with the optimal score parameters. The selection criterion of the AI models was defined as a C-index ≥ 0.7 . Based on the AI models, the predictive performance (censored C-index and mean cumulative/dynamic area under the receiver operating characteristic curve [auROC]), calibration curves, and Brier score (BS) were evaluated. The BS represents the mean square difference between observed patient status and predicted survival probabilities; it ranges from 0 to 1 and is negatively correlated with the discrimination and calibration of algorithms. IBS is defined as an overall estimation of BS; a value lower than 0.25 is deemed applicable in the clinic ^[8].

4. Model estimation

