An ensemble model was developed and named the precise treatment allocation (PTA) model in our study. It could accurately predict the survival probability of each patient by alternating the different treatments. The inputs of the PTA model mainly comprise four modules: (a) liver function, such as serum albumin, serum bilirubin, and coagulative function indexes; (b) tumor burden, including serum alpha-fetoprotein (AFP), tumor size, and tumor number; (c) demographic data, such as age and gender; and (d) routine laboratory indications, such as routine blood examination and kidney function indexes. To further estimate the predictive performance of the PTA model, it was compared with other prognostic models, including widespread clinical guidelines (BCLC, BCLC B sub-classification ^[9], HKLC, and the most recent Italian Liver Cancer [ITA.LI.CA] staging system ^[10]), other tumor-burden-based models (up-to-seven model ^[11], four-and-seven model ^[12], and six-and-twelve model ^[13]), and models incorporating other parameters (hepatoma arterialembolization prognostic [HAP] score, modified HAP [mHAP] II score ^[13], mHAP III score ^[14], albumin-bilirubin [ALBI] score ^[15], and the model to estimate survival in ambulatory HCC patients [MESIAH] ^[16]), by estimating the auROC and C-index.

Here, HCC patients could achieve two potential survival rates and predicted median survival times (MSTs) by choosing TACE or LR. The ideal LR candidate is defined as a patient whose MST could be extended by more than 50% compared with the MST of primary treatment if LR is adopted in the model. Similarly, ideal TACE candidates are those with an additional survival benefit of more than 50% compared to LR allocation in TACE prediction time. Considering that BCLC and HKLC ^[17] have clearly defined LR and TACE candidates, the ideal LR and TACE candidates of the PTA model were compared with candidates recommended by these two widely used guidelines.

5. Web implementation

After train and validation, the optimized PTA model was implemented as a web

interface, which generates the MST and depict integrated survival curves composed of LR and TACE according to the clinic parameters of specific patients provided by users. Relative algorithms of web development were described in the supplement 1.

6. Statistical analyses

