LR group (4.60 [3.00;7.00] cm) than in the TACE group (6.30 [4.00;9.90] cm); (b) The tumor lesions of HCC were relatively few in the LR group (1.0 [1.0-1.0] lesion) than in the TACE group (1.0 [1.0-2.0] lesions). In addition, the liver function of HCC patients (CPS and Child-Pugh stage) varied remarkably between the LR and TACE groups. A higher proportion of Child stage B patients were included in the TACE group (17.6%) than in the LR group (11.1%). The median follow-up was 54.0 months (IQR 38.7–69.2 months) for LR therapy and 36.1 months (IQR 24.7–54.7 months) for TACE. The 1-year, 3-year, and 5-year survival probability was 91.7%, 79.6%, and 70.8% for LR allocation, respectively, while 74.8%, 41.5%, and 26.4% for TACE treatment, respectively. Although there were significant differences between the LR and TACE groups, we perceived therapy type as a pivotal factor in the AI models to simulate a real-world clinical setting, considering the precise prediction of AI technologies.

Selection of the optimal AI model

We applied 10 kinds of machine learning survival algorithms in the train cohort, of which seven AI models performed well, with the C-index > 0.7 , and were retained: (i) random survival forest (RSF), (ii) conditional survival forest, (iii) DeepSurv algorithm, (iv) Extra Survival Trees, (v) Gompertz, (vi) standard Cox proportional hazards model (CoxPH), and (vii) PTA model based on the above six models. For model estimation, the C-index and IBS of these seven AI models were displayed in the Table 2. The C-index of the PTA model was 0.854 and 0.801 in the train and validation cohorts, respectively, which were higher than other six AI models except for the RSF model in train cohort. Even though the RSF model achieved the highest C-index (0.926) in the train set, while in the validation cohort, the C-index was only 0.765, indicating the potential presence of over-fitting in the RSF model. Given the C-index of the train and validation cohorts, the PTA model derived from the above six algorithms outperformed other single-algorithm models. As expected, the IBS of the six single algorithms and PTA algorithm was far smaller than 0.25, demonstrating their capability for clinical application (Supplement 2-3).

Predictive performance of the PTA model

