the LR and TACE candidates were determined following the BCLC and HKCL guidelines. Among the patients who underwent LR therapy (Supplement 6A-C), the PTA model identified 1386 potential LR candidates, BCLC guidelines selected 1196 cases, and HKCL chose 1765 candidate patients. K-M cures clearly showed that the survival difference between recommended and non-recommended populations was the largest in the PTA model compared with other guidelines. Meanwhile, the hazard ratio (HR) calculated by Cox regression analysis was 10.6, 2.02, and 1.93 respectively in the PTA model, BCLC, and HKCL guidelines (non-recommended as reference). Likewise, among the patients who accepted TACE, the PTA model, BCLC, and HKCL guidelines discriminated 323, 964, and 521 cases, respectively. The HR for the PTA model, BCLC, and HKCL guidelines was 25.4, 0.901, and 0.503, respectively (Supplement 6D-F).

Moreover, the LR candidates recommended by the PTA model had a prolonged OS compared to those suggested by BCLC and HKLC (Figure 2A); a similar conclusion was reached for the TACE group (Figure 2B). Intriguingly, the PTA model also found potential allocation “error” populations in the TACE and LR groups, depicted as hypothetical K-M curves (Figure 3A-B). The MST predicted by the PTA model was significantly higher compared with that of the original therapy allocation, suggesting that alternative therapies can enable patients to achieve a better prognosis and that mistaken allocation either to LR or TACE is still abundant. The patients with actual treatment and LR or TACE candidates are clearly shown in Figure 3C. Regarding the original LR allocation, 1458 cases had the right allocation, while 458 “model-found” cases were misled and should have been given TACE therapy. Similarly, there were abundant erroneous allocations among the original TACE allocations (2752, 89.5%).

Given that BCLC, the HKLC staging system, and PS could affect the prognosis of the potential benefit-gained population, we stratified patients into different BCLC subgroups (BCLC 0-A, BCLC B, and BCLC C stages; Supplement 7), HKLC subgroups (HKLC I-II and HKLC III; Supplement 8), and different PS (PS0 and PS1; Supplement 9). The PTA model could accurately select benefit-gained patients for LR

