and TACE across different BCLC and HKLC stages and PS. Collectively, the K-M curves and HR consistently showed that the PTA algorithm could more effectively select TACE and LR candidates than the two authoritative therapeutic guidelines.

Web development and clinical application

To make an easy-to-apply tool and visualize the individual predictive results, we implemented the PTA models as a web interface, which could be freely accessed from www.pta4hcc.com. Users may input four groups of parameters: (a) demographic information, such as age and gender; (b) liver function; (c) tumor burden files; and (d) routine laboratory results like kidney function. The PTA model calculates the survival rate for each month when adopting different treatments (now including LR and TACE) and generates MST, all of which can be displayed on the user-friendly interface. For example, a 65-year-old man with hepatitis B virus infection and no prior treatment would possess a better prognosis if LR therapy was adopted instead of TACE after the diagnosis of HCC. His tumor burden characteristics are as follows: the number of tumors is four, the maximum tumor size is 8 cm, the AFP is 300 µg/L, and the ECOG or PS is 0. In addition, the information on the other two groups is also input into the website in the complete version. The output is his predicted survival curves derived from the PTA model, showing that LR's MST is 78 months, while TACE's MST is only 23 months (Supplement 10).

In parallel with the complete PTA algorithm, a concise version including the nine most important features was also developed on this website. This simple AI version could also calculate the integrated survival model immediately upon the input of these important features, especially for cases where some above-stated module features were unavailable. For example, a patient with two tumor lesions, a tumor size of 12 cm, 100 µg/L AFP, good PS, 120 g/L HGB, 35 U/L AST, 40 g/L ALB, and normal INR would benefit from TACE therapy rather than LR. The simulative survival curve indicates that the MST was 15 and 10 months for TACE and LR allocation, respectively (Supplement 11).

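### The counts of wrongly allocated patients (458 LR, 2752 TACE) are causal claims read off a prediction model, with no adjustment, overlap or confounding analysis to support them

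*Combined protocol and SAP*

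**What the plan says.** Section 4 (Model estimation) says of the PTA model: "It could accurately predict the survival probability of each patient by alternating the different treatments". Each patient thus gets two predicted median survival times (MSTs), one per treatment. A patient is an ideal candidate for a treatment if its predicted MST is more than 50% longer.

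On inputs, the same section says "The inputs of the PTA model mainly comprise four modules": liver function blood tests, tumour burden (AFP, size, number), demographics and routine laboratory values. Section 2 (Treatment procedures) says that LR operators explored tumour location and vascular anatomy, then "assessed the distance between lesions, and ensured residual liver volume". It mentions ICG clearance where multiple tumours are resected.

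The Results (Basic clinical characteristics) concede the imbalance ("Although there were significant differences between the LR and TACE groups"). The answer offered in the same sentence is that "we perceived therapy type as a pivotal factor in the AI models to simulate a real-world clinical setting", on the ground that AI technologies predict precisely.

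The Results (Comparison with clinical guidelines) then conclude that, among LR patients, 458 "cases were misled and should have been given TACE therapy", and that "there were abundant erroneous allocations among the original TACE allocations (2752, 89.5" per cent).

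**The concern.** To say that a patient should have had the other treatment is to make a claim about survival under a treatment that the patient did not receive. A model can predict survival very well under the treatment given and still be wrong when the treatment input is switched, because clinicians chose the treatment partly on prognosis.

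Nothing reported tests the switched prediction. The C-index, AUC, integrated Brier score and calibration compare predictions with outcomes under the treatment received. The hazard ratios of 10.6 (LR patients) and 25.4 (TACE patients) compare recommended with non-recommended patients who all had the same treatment, so they show prognostic separation and not benefit from switching. The hypothetical survival curves for the supposed allocation errors are themselves model output.

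Section 6 (Statistical analyses) lists two-sample tests, Kaplan–Meier curves and log-rank tests. It has no propensity score, weighting, matching, overlap check or sensitivity analysis for unmeasured confounding.

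At stake is the study's main message, and a freely accessible website that shows users both predictions side by side.

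**Working it through.** **1. The plan's counts reproduce** (Results, Basic clinical characteristics and Comparison with clinical guidelines).
- LR: 1458 + 458 = 1916; 458/1916 = 23.9%.
- TACE: 2752/3075 = 89.5%.
- Together: (458 + 2752)/4991 = 3210/4991 = 64.3% of the cohort labelled wrongly allocated.

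**2. How the 2752 arises.** The PTA model picked 323 TACE candidates among TACE-treated patients, and 3075 − 323 = 2752 exactly. The count therefore behaves as everyone who is not a TACE candidate. A TACE patient with equal predicted MSTs, or with TACE better by less than 50%, would be counted as an error.

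**3. Size of the crude contrast.** With survival S at each time, the crude TACE:LR hazard ratio is ln(S_TACE)/ln(S_LR).
- 1 year: ln(0.748)/ln(0.917) = 3.35
- 3 years: ln(0.415)/ln(0.796) = 3.85
- 5 years: ln(0.264)/ln(0.708) = 3.86

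This mixes treatment effect with selection. The documents do not allow the two to be separated.

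**4. Can confounding alone move a ratio of medians past 1.5?** The following inputs are assumptions. Suppose no treatment effect, and one unmeasured adverse factor present in 5–20% of LR and 40–80% of TACE patients, which multiplies the hazard by h = 1.5 to 4. Each group's median t solves p·exp(−λht) + (1 − p)·exp(−λt) = 0.5, where p is the prevalence; λ cancels in the ratio.
- Spurious LR:TACE median ratio over all scenarios: 1.09 to 3.02.
- At h = 3: 1.28 to 2.37.

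So it can cross 1.5, but not in every scenario. Under the complement rule of step 2, a bias B towards LR means that the true TACE:LR ratio must exceed 1.5 × B before a patient escapes the error label: 1.5 × 1.09 = 1.64 up to 1.5 × 3.02 = 4.53.

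**5. Extrapolation in time.** LR survival is still 70.8% at 5 years. Constant hazards through the stated LR survival, median = t·ln 2/(−ln S), give 96, 109 and 120 months from the 1-, 3- and 5-year figures. All exceed the upper quartile of LR follow-up, 69.2 months. This concerns the LR group as a whole; a high-risk patient's LR median can fall inside follow-up.

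**6. Size of a validation check.** If the overall proportions carry over (assumption), the TACE-preferred class among the 799 validation patients holds about 294 × 458/1916 = 70 LR patients and 505 × 323/3075 = 53 TACE patients.

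**The case against.** Several objections are fair and limit the point.

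- **The inputs may be fuller than listed.** The list is worded as the main modules with examples, and the website example includes performance status, which is in none of the four. Supplement 1 was not available. A reader might infer that anatomy, liver volume and ICG clearance were left out. The documents show only that they are not listed. That they drove the choice of treatment is also an inference: Section 2 describes them as part of the operation.
- **The groups overlap on what is reported.** Eligibility already restricts liver function, performance status and vascular invasion. Size interquartile ranges overlap (3.00–7.00 and 4.00–9.90 cm), and the median tumour number is 1 in both groups. A reader might take the website case, where "the number of tumors is four, the maximum tumor size is 8 cm", as lying outside the LR data. It lies above the LR upper quartiles (1 tumour, 7 cm), which does not show that comparable LR patients are absent.
- **Unmeasured resectability does not explain the 458.** It would favour LR and so reduce TACE recommendations.
- **The pattern is not shown to be reversed.** A reader might contrast TACE preference in 23.9% of LR patients with 323/3075 = 10.5% of TACE patients. The two counts may use different rules: 1458 right allocations and 1386 LR candidates differ by an unexplained 72.
- **The wording is partly hedged.** The text speaks of potential errors and hypothetical curves.

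What remains is that the conclusions on who should have had which treatment are stated without hedging and without any causal analysis behind them.

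**Conclusion.** The point stands in a bounded form. The plan acknowledges confounding, does not address it, and reports causal counts covering 64.3% of the cohort. For the 2752, two mechanisms are plausible: residual confounding favouring LR, against a crude hazard ratio of 3.35 to 3.86, and a label that appears to absorb patients with no clear preference. For the 458, model error or unchecked extrapolation fits better.

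A reader might go further and infer that a null treatment effect would label the typical TACE patient an error unless the inputs removed some fixed share of the crude contrast. The documents do not support that. The count follows the complement of the TACE candidates, not a 1.5-fold LR advantage, and any such share depends on an LR median extrapolated to anywhere from 96 to 120 months. Nor do the documents show that the counts are wrong; they show that the counts are unsupported. A corrected count needs patient data.

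**What to change.** 1. **Wording and counting.** List all model inputs. Replace the language of misdirection and error with *predicted by the model to live longer under the other treatment*. Count only patients who meet the stated 50% rule in favour of the other treatment, and report the rest as *no clear preference*.
2. **Overlap.** Fit a propensity model for LR versus TACE on all PTA inputs plus centre and calendar year, and show its distribution by treatment. Limit the allocation counts and the website comparison to a region of overlap fixed in advance.
3. **Test of the switched prediction.** In the 799 validation patients, within each PTA recommendation class, compare overall survival between those who received LR and those who received TACE, using overlap weights. Give the hazard ratio, confidence interval and E-value. State three limits: estimates will be imprecise (about 70 LR and 50 TACE patients in the TACE-preferred class, if proportions carry over); this set also informed the choice of the PTA model; and weighting cannot remove unmeasured confounding.
4. Keep causal wording only if step 3 supports it.

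The cost is extra analysis of existing data and some rewording; the learner itself is unchanged. Fewer patients will receive a two-treatment comparison, and the counts will probably fall.

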Cover page

Trial Title:

**A New Conception About Individualized Treatment
Allocation for HCC—Using Machine Learning**

**Unit of Study: The Second Affiliated Hospital of Air
Force Military Medical University**

Principal Investigator: [name]

Date: 2023-8-20

NCT number and document date have not been assigned

Study protocols

1. Study population

Between January 2010 and October 2021, a total of 5816 consecutive HCC patients receiving LR or TACE from 15 Chinese tertiary hospitals were retrospectively screened. HCC was diagnosed based on either imaging or pathological results as previously described [1]. To better fit LR and TACE therapies into AI models, liver-confined HCC was incorporated with LR or TACE candidates according to the latest criteria of the BCLC guidelines [2]. Patients with well-preserved liver function, good PS (Eastern Cooperative Oncology Group [ECOG] PS0), and no vascular invasion or extrahepatic spread were divided into BCLC 0, A, and B stages, where they could undergo LR and TACE therapy. In addition, mild tumor-related symptoms (PS1) have not been an absolute contraindication for LR as per recent research [3], and the guidelines of the American Association for the Study of Liver Diseases (AASLD) expanded the PS 0–1 in the BCLC 0–B stage, considering the conceptual overlap between them [4, 5]. Here, the inclusion criteria were as follows: (a) diagnosed with HCC; (b) receiving LR or TACE therapy; (c) complete clinical information; (d) preserved liver function (Child-Pugh Score [CPS] ≤ 7); and (e) PS 0–1. The exclusion criteria included: (a) vascular invasion or extrahepatic spread; (b) decompensated liver cirrhosis (gastrointestinal bleeding, ascites, or hepatic encephalopathy); (c) younger than 18 years; and (d) duration of follow-up of fewer than 30 days. Image assessment, including the diameter of the largest nodule (tumor size, measured in centimeters) and tumor number, was performed by two independent investigators via CT or MRI. The flow chart of the study is depicted in Figure 1. Eligible patients were randomly stratified into train and validation cohorts (ratio=0.85: 0.15). The study was approved by the committee on human research of participating centers and approved by the Medical Ethics Committee of the Tangdu hospital (TDLL-202302-06) and Daping Hospital of the Army Medical University (2022(186)). Written informed consent to participate in this study was provided by the participants' legal guardian/next of kin.

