Continuous and normally distributed variables were expressed as mean with a standard difference (SD) and compared using Student's t-test, while non-normally distributed variables were presented as median with interquartile range (IQR) and compared using the non-parametric Mann–Whitney U test. Categorical variables were expressed as numbers and percentages and tested by Fisher's exact test or the χ^2 test.

Overall survival (OS) was defined as the time interval between initial TACE or LR and all-cause death. Patients who survived up to the last follow-up date (October 15th, 2021) or were lost to follow-up were censored. Survival curves were displayed using the Kaplan–Meier (K-M) method and compared with the log-rank test.

Python software was applied for train AI models and detailed codes were uploaded as supplements (<https://github.com/ApocalypseZ/Survival>). R software and related packages (survival, rms, reportROC, survminer, and ggplot2) were adopted to conduct statistical analysis and plot figures. $P < 0.05$ was considered statistically significant.

Results information for studies

Basic clinical characteristics

In this multicenter study, 4991 patients met the selection criteria and were included. Of these, 1916 patients (38.39%) were amenable to LR while 3075 patients (61.61%) submitted to TACE (Figure 1). 4192 (84%) and 799 (16%) patients were divided into train and validation sets, respectively. Among train set, 1622 (38.7%) were underwent LR while 2570 (61.3%) adopted TACE treatment. In validation set, 294 (36.8%) and 505 (63.2%) were allocated to LR and TACE treatment, respectively. The demographic and clinicopathological characteristics of the cohort are shown in Table 1. The variables associated to tumor burden were lower in the LR group than those of the TACE group in overall cohort: (a) The largest tumor diameters were smaller in the

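### The 0.7 C-index screen appears to use apparent training values, and PTA's claimed superiority rests on the validation C-index, reported without a CI or paired comparison

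*Combined protocol and SAP*

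**What the plan says.** Section 3 (Model development) sets the rule without naming the data it applies to: "The selection criterion of the AI models was defined as a C-index ≥ 0.7". It describes cross-validation as the safeguard against overfitting: "the AI algorithms in the training cohort were developed by adopting K-fold cross-validation". Its stated use is tuning, followed by a refit: "hyperparameter optimization was tuned by an exhaustive cross-validation grid search, and the models were refitted in the training set".

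There are only two data sets. Section 1 (Study population) says: "Eligible patients were randomly stratified into train and validation cohorts (ratio=0.85: 0.15". Basic clinical characteristics gives the sizes: "4192 (84%) and 799 (16%) patients were divided into train and validation sets, respectively".

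The results under Selection of the optimal AI model place the screen in the training data: "We applied 10 kinds of machine learning survival algorithms in the train cohort, of which seven AI models performed well". The criterion there is written as above 0.7, whereas Section 3 has at least 0.7. The same section reports that "the RSF model achieved the highest C-index (0.926) in the train set", gives 0.765 for RSF in validation, and itself raises possible overfitting. RSF nevertheless remains one of the six members of PTA. PTA is given 0.854 in training and 0.801 in validation, and the section concludes: "Given the C-index of the train and validation cohorts, the PTA model derived from the above six algorithms outperformed other single-algorithm models".

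**The concern.** There are two linked weaknesses.

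- **The screen.** A minimum C-index guards against overfitting only if it is computed on data that the model has not been fitted to. On fitted data, overfitting raises the C-index, so the models most in need of screening pass most easily.
- **The comparison.** If training C-indices are apparent values, they carry no usable information on which model is best. The ranking then rests on the 799 validation patients, whose C-index is also presented as PTA's performance. No test set, nested validation or optimism correction is described, and no CI or paired difference for the C-index appears in the text.

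What is at stake is the evidence that the ensemble improves on its components, and the independence of 0.801. The results under Predictive performance of the PTA model do not name the cohort behind their AUCs. That leaves 0.801 as the only PTA discrimination figure in the text explicitly labelled as validation. PTA is also the model placed on the public website.

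**Working it through.** **Inputs from the document.** Training n = 4192 and validation n = 799. C-index for RSF: 0.926 training, 0.765 validation. C-index for PTA: 0.854 training, 0.801 validation. Overall AUC CIs: 0.887–0.938, 0.891–0.937 and 0.903–0.953.

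**Assumptions.** The standard error (SE) of a validation C-index and the correlation between models' C-indices are not given, so ranges are used.

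**1. Plan's own figures.** 4192 + 799 = 4991, and 4192/4991 = 84.0%, as stated. The C-indices cannot be recomputed without patient data.

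**2. Drop from training to validation.**
- RSF: 0.926 − 0.765 = 0.161
- PTA: 0.854 − 0.801 = 0.053

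**3. Plausible SE at n = 799.** Simulated exponential survival with about 48% events gives an SE of about 0.010 to 0.012 for a C-index near 0.80. The AUC CI widths divided by 3.92 give:
- 0.051/3.92 = 0.0130
- 0.046/3.92 = 0.0117
- 0.050/3.92 = 0.0128

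These are only a rough guide, because the AUC cohort is not named. A range of 0.010 to 0.016 covers both sources.

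**4. Could 0.926 be an out-of-fold value?** 0.161/0.016 = 10.1 and 0.161/0.010 = 16.1. Under a random split, an out-of-fold estimate should not exceed the validation value by 10 to 16 SEs. The figure behaves like an apparent C-index after refitting. RSF and PTA are reported in the same table, so the same reading applies to PTA's 0.854.

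**5. What decides the ranking.**

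| | Training | Validation |
|---|---|---|
| RSF | 0.926 | 0.765 |
| PTA | 0.854 | 0.801 |
| PTA − RSF | −0.072 | +0.036 |

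Training favours RSF, and only the validation column favours PTA. The other five single-model values are in a table that is not reproduced in the text, so PTA's lead over the runner-up is unknown.

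**6. Selection optimism if the best of seven is picked on the 799.** With seven truly equal models, the expected excess of the winner is 1.352 × SE × √(1 − ρ), where 1.352 is the expected maximum of seven independent standard normals.
- Low end: 1.352 × 0.010 × √0.1 = 0.0043
- High end: 1.352 × 0.015 × √0.5 = 0.0143

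If PTA truly leads all six others, Monte Carlo over the same ranges (SE 0.010 to 0.015, ρ 0.5 to 0.9) gives:
- true lead 0.02: about 0.000 to 0.008
- true lead 0.036: about 0.000 to 0.0016 (0.0023 if SE is 0.016 and ρ is 0.5)

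If PTA was fixed in advance as the final model, this component is zero.

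**7. Did the screen make a wrong decision?** RSF's validation value of 0.765 exceeds 0.7, so an out-of-sample floor at the same level would also have kept it.

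**The case against.** The strongest reply is that PTA was not a best-of-seven winner. Section 4 (Model estimation) presents the ensemble as the study's model, and the prognostic comparisons, the guideline comparison and the web tool all concern it. The quoted sentence says that PTA outperformed the others, not that it was chosen for that reason. This stands as a real possibility. However, the section heading speaks of selecting the optimal model, and nowhere is PTA said to have been fixed before the 799 were examined. Even if it was, the superiority statement still needs paired intervals.

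A second reply is that the screen may have used the cross-validation score while the printed table shows refit values. Details are assigned to Supplement 1 and to uploaded code, neither of which is available here. The text does not say so, and the only training values printed point the other way. One sentence from the sponsor would settle it.

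Three stronger readings are tempting but unsupported.

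- A reader might infer that 0.801 is materially inflated. The upper end, about 0.014, requires all seven models to be truly equal. With a real lead of the size seen against RSF, the bias is about 0.002 or less.
- A reader might infer that nearly uninformative models were admitted, by subtracting RSF's drop from the threshold (0.70 − 0.161 = 0.539). That transfers the drop of the model with the highest training C-index to a hypothetical one. No such model is documented, and three of the ten algorithms were dropped.
- A reader might infer that including RSF harmed PTA. PTA exceeds RSF in validation and has the smaller drop. A lenient training screen does not by itself bias a C-index measured on held-out patients.

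The document is also open about RSF: it prints both values and raises overfitting itself.

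**Conclusion.** The point holds in a limited form. The 0.7 rule, as reported, works on training values that are almost certainly apparent, so it cannot screen out overfitting, and the training C-indices should not be cited as evidence for ranking PTA against its components. The superiority statement therefore depends on the validation C-index, which doubles as PTA's reported performance and is given without a measure of uncertainty.

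The numerical consequence for 0.801 is probably small, on the ranges in the working. These rest on assumed SEs and correlations, and on a runner-up value that the text does not show. The documents do not show that a model was wrongly retained or that 0.801 is far off. The defect lies in what the rule can detect and in how independent the estimate is. It should be corrected because the remedy needs only existing data.

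**What to change.** **In Section 3:** state that the 0.7 rule, the choice of ensemble members and weights, and the choice of final model all use out-of-fold C-indices from cross-validation within the 4192 training patients. Nest the cross-validation, so that scores are not flattered by the grid search. Use one form of the threshold throughout.

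**In the results:** replace the apparent training C-indices with the out-of-fold values. Report 0.801 with a bootstrap CI. Add paired bootstrap CIs for PTA minus each single model in the 799.

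**Disclosure:** say that the 799 had already been seen when PTA was preferred, or state that PTA was pre-designated as the final model. The 799 cannot now serve as an untouched test set. Moving the 0.7 floor to them would not help either, since that would add another selection step on the same patients.

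**Cost:** some refitting, particularly for the ensemble, because the documents do not say that out-of-fold predictions were kept. The training C-indices will probably fall and the set of retained models may change. No new patients are needed.
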